- Treatment-related deaths that occur during study treatment through 28 days following the last dose of any study treatment, or the beginning of another anti-cancer therapy, whichever occurs first.
- Drug-induced liver injury (Hy’s Law cases), confirmed as detailed in Section 8.6.2, that occurs during study treatment through 28 days following the last dose of any study treatment, or the beginning of another anti-cancer therapy, whichever occurs first.

- Grade ≥ 3 non-hematologic treatment-related AEs in the first cycle of treatment that have failed to recover to baseline or \leq Grade 1 within 21 days from when the second cycle is due to start (corresponding to recovery before or/on Day 49 of the first cycle) and required permanent discontinuation of study treatment.
- Grade 4 treatment-related neutropenia ($ANC < 500/mm^3$) lasting ≥ 42 days from the start of cycle 1 in the presence of bone marrow hypoplasia without evidence of active AML or MDS.

A safety event of interest is defined as any of the above deemed related to glasdegib and /or azacitidine as assessed by the investigator. All AEs will be classified according to CTCAE version 4.03.

The safety stopping criteria will be applied within a cohort (AML or MDS) starting when at least 10 patients have completed the required follow-up period (28/24 weeks for MDS/AML respectively) and applied continuously afterwards. Enrollment will continue unless the stopping boundary is crossed (Table 10). The same stopping criteria will be used for the AML and MDS cohorts; however, the two cohorts will be analyzed independently.

Table 8. MDS Efficacy Decision Criteria

# Patients with mature response data (inclusive)	Stop expansion MDS enrollment if there are this many responses total:
1-9	No stop
10-13	≤ 2
14-16	≤ 3
17-20	≤ 4
21-24	≤ 5
25-27	≤ 6
28-29	≤ 7
30	Full enrollment

Table 9. AML Efficacy Decision Criteria

# Patients with mature response data (inclusive)	Stop expansion AML enrollment if there are this many responses total:
1-10	No stop
11-13	0
14-17	≤ 1
18-20	≤ 2
21-23	≤ 3
24-27	≤ 4
28-29	≤ 5
30	Full enrollment

[figure not shown]
Table 10. Safety Decision Criteria

# Patients*	Stop cohort enrollment if there are this many patients with any pre-defined safety events of interest**
1-9	No stopping
10-12	≥4
13-16	≥5
17-20	≥6
21-23	≥7
24-27	≥8
28-30	≥9

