5.4.5.1. Glasdegib

Glasdegib does not need to be delayed or dose reduced for hematologic toxicity deemed unrelated/unlikely related to glasdegib by the Investigator.

Patients experiencing Grade 3 or 4 non-hematological toxicities potentially attributable to glasdegib should have their glasdegib treatment interrupted regardless of when it occurs in the cycle until the toxicity resolves or returns to baseline or \leq Grade 1, as described in [Table 13](#). If these parameters have not been met following >28 consecutive days of dose interruption, glasdegib should be permanently discontinued. If glasdegib treatment is permanently discontinued, patients may continue single agent treatment with azacitidine, if according to the investigator's judgment a clinical benefit has been observed, and following discussion between the investigator and the sponsor.

Appropriate follow-up assessments should be implemented until adequate recovery (toxicity resolves or returns to baseline) occurs.

Depending on when the adverse event resolved, treatment interruption may lead to the patient missing all subsequent planned doses of glasdegib within the cycle. If the AE leading to

treatment interruption recovers within the same cycle, re-commencement of dosing in that cycle is allowed. The need for a dose reduction at the time of treatment resumption should be based on the criteria outlined in [Table 13](#), unless specifically agreed otherwise following discussion between the Investigator and the Sponsor. If a dose reduction for glasdegib is applied in the same cycle, the patient must return to the clinic to receive a new supply of drug. Glasdegib doses omitted for toxicity will not be replaced within that cycle (eg, cycles will not be prolonged beyond the 28 days in order to make up for any missed glasdegib doses during that cycle).

Glasdegib may be interrupted or permanently discontinued for any reason as per good clinical practice. In the event of glasdegib treatment interruption for reasons other than treatment-related toxicity (eg, elective surgery) for a duration >28 days, the details of treatment resumption will be determined in consultation with the Sponsor.

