Dose reduction of glasdegib by 1 or, if necessary, 2 dose levels (Table 12) will be allowed depending on the type and severity of toxicity encountered. **NOTE:** In the specific situations where clinical benefit is observed, glasdegib can be reduced below 50 mg QD upon Sponsor approval. All dose modifications/adjustments must be clearly documented in the patient's notes and case report form (CRF).

Once the glasdegib dose has been reduced, all subsequent cycles should be administered at that dose level, unless further dose reduction is required. Dose re-escalation is not allowed. Deviations from any of the dose modifications must be discussed and agreed with the Sponsor Medical Monitor.

Table 12. Available Dose Levels

Glasdegib (mg QD)
100
75
50
25 *

* **NOTE:** If clinical benefit is observed, glasdegib may be reduced below 50 mg QD following Sponsor approval.

Dose modifications for treatment-related non-hematologic toxicities (excluding QTc prolongation, muscle spasms, and myalgia) are outlined in [Table 13](#).

Table 13. Dose Modifications for Non Hematologic Toxicities (Excluding QTc Prolongation, Muscle Spasms, and Myalgia)

Toxicity (NCI CTCAE version 4.03)	Glasdegib

≥ Grade 3 toxicity (Nausea, vomiting, and/or diarrhea must persist at ≥ Grade 3 (despite maximal appropriate medical therapy) to require dose modification)
	
Hold glasdegib until toxicity has recovered to ≤ Grade 1.
 
First episode: Decrease by 1 dose level
 
Second episode: Decrease by 1 dose level
 
Third episode: Permanently discontinue

Potential drug induced liver injury/Hy's Law (as defined in Section 8.6.2)
	
Interrupt glasdegib dosing. If an alternative cause is found, restarting of glasdegib at the same dose may be considered.

Confirmed drug induced liver injury/Hy's Law (as defined in Section 8.6.2)
	
Glasdegib should be permanently discontinued.

Patients should be closely monitored for potential cardiovascular symptoms. Appropriate monitoring should include clinical examinations, vital signs, routine ECGs, and AE monitoring. In case of QTc prolongation, concomitant conditions such as electrolyte imbalances, hypoxia, or use of medications affecting the QT interval should be ruled out and/or corrected. In case of clinically significant toxicities, glasdegib administration should be interrupted and the dose reduced as indicated in Table 14.

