Concomitant administration of glasdegib with moderate/strong CYP3A4/5 inhibitors (Appendix 6 and Appendix 7) and drugs with known risk of Torsade de Pointes (TdP) (Appendix 5) is not recommended due to the potential for drug-drug interaction to prolong the QTc interval. However, if it is medically necessary for patients to use these medications please refer to Section 7.6 for monitoring procedures. All protocol specified QTcF prolongation-related exclusion criteria must be followed. Investigators must be aware of the QTcF-prolonging potential of all medications that patients on study are taking, and should take appropriate action when clinically indicated. Given the potential for QTcF prolongation, the measurement and immediate correction of electrolyte abnormalities such as potassium

and magnesium, and of other reversible causes of QTcF prolongation such as hypoxia, are especially important. In the event that the QTcF interval is prolonged beyond 480 ms (CTCAE v.4.03 \geq Grade 2), Table 14 must be referenced and actioned. Additional ECG and cardiac consultation should be obtained if clinically indicated.

Table 14. Glasdegib Dose Modifications for mean QTcF (mQTcF) Prolongation

CTCAE v 4.03	Grade 1	Grade 2	Grade 3**	Grade 4	
Electrocardiogram QT corrected (QTc) interval prolonged*	450-480 msec	481-500 msec	≥ 501 msec at least two separate ECGs	QTc ≥ 501 or >60 msec change from baseline and Torsade de pointes or polymorphic ventricular tachycardia or signs/symptoms of serious arrhythmia	
*The severity of QTc prolongation assessment is to be done by calculating a mean QT of 3 consecutive ECGs performed approximately 2 minutes (but no longer than 5 minutes) apart by using the Fridericia correction method (mQTcF). ** If mQTcF is ≥ 501 msec, continuous ECG monitoring and cardiology consultation are required.					
Category	Requirement	Grade			
		1	2	3	4
ECG monitoring	Continuous ECG monitoring and cardiology consultation for mQTcF ≥ 501 msec			x	x
Initial glasdegib action	Discontinue and do not re-challenge.				x
	Interrupt treatment		x	x	
	Continue at same level	x			
General management	Assess and correct electrolyte abnormalities.	x	x	x	x
	Withhold any concomitant medications (if possible) that may cause QTc prolongation.		x	x	x
Resume glasdegib dosing	At prior dose if mQTcF returns to ≤ 470 msec and to within 20 msec of baseline in 7 days and if no prior dose interruption related to mQTcF prolongation has occurred		x	x	

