Glasdegib	
Continue at same dose level.
 
Administer oral rehydration solutions containing electrolytes.^a
 
Consider other appropriate interventions (eg, anti-spasmodics) as per institutional guidelines.
 
Evaluate levels of: CK, Vit B6, Vit D, ferritin, transferin and electrolytes (Na, K, Mg, Ca and P).^b
 
If CK is elevated, evaluate urine and serum myoglobin, CK isoenzymes, and serum creatinine.
	
Continue at same dose level.
 
Administer oral re-hydration salts containing electrolytes.^a
 
Consider other appropriate interventions (eg, anti-spasmodics) as per institutional guidelines.
 
Evaluate levels of: CK, Vit B6, Vit D, ferritin, transferin and electrolytes (Na, K, Mg, Ca and P).^b
 
If CK is elevated, evaluate urine and serum myoglobin, CK isoenzymes, and serum creatinine.
 
If event persists, hold dose until resolution to Grade ≤ 1.
 
Upon resolution, restart at prior dose, or for prolonged muscle spasms, consider reducing dose by one dose level.
	
Hold dose.
 
Administer oral re-hydration salts containing electrolytes.^a
 
Consider other appropriate interventions (eg, anti-spasmodics) as per institutional guidelines.
 
Evaluate levels of: CK, Vit B6, Vit D, ferritin, transferin and electrolytes (Na, K, Mg, Ca and P).^b
 
If CK is elevated, evaluate urine and serum myoglobin, CK isoenzymes, and serum creatinine.
 
Upon resolution to Grade ≤ 1, restart study treatment at next lower dose level.
 
If the event does not resolve within 3 weeks to Grade ≤ 1, at the discretion of the Investigator the dose may be restarted at the next lower dose level or the patient may be permanently discontinued from study treatment.

Abbreviations: CK creatinine kinase; Vit vitamin; Na sodium; K potassium; Mg magnesium; Ca calcium; P phosphorous.
 
a. Electrolyte replacement drinks should include Na, K, Mg, Ca and P. Consideration should be given to ensuring adequate hydration prior to bedtime, and whenever fluid intake is decreased for a prolonged duration.
 
b. Labs may be drawn as unscheduled assessments between protocol visits.
 
In the event of alopecia or dysgeusia, investigator discretion should be applied with respect to dose interruption and/or dose reduction of glasdegib as preliminary analysis of available clinical data suggests that these events are not dose dependent.
			

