8.6.2. Potential Cases of Drug-Induced Liver Injury

Abnormal values in aspartate aminotransferase (AST) and/or alanine aminotransferase (ALT) levels concurrent with abnormal elevations in total bilirubin level that meet the criteria outlined below in the absence of other causes of liver injury are considered potential cases of drug-induced liver injury (potential Hy's law cases) and should always be considered important medical events.

The threshold of laboratory abnormalities for a potential case of drug-induced liver injury depends on the patient's individual baseline values and underlying conditions. Patients who present with the following laboratory abnormalities should be evaluated further to definitively determine the etiology of the abnormal laboratory values:

- Patients with AST or ALT and total bilirubin baseline values within the normal range who subsequently present with AST or ALT values ≥ 3 times the upper limit of normal (X ULN) concurrent with a total bilirubin value ≥ 2 X ULN with no evidence of hemolysis and an alkaline phosphatase value ≤ 2 X ULN or not available.
- For patients with preexisting ALT **OR** AST **OR** total bilirubin values above the ULN, the following threshold values should be used in the definition mentioned above:
 - For patients with preexisting AST or ALT baseline values above the normal range: AST or ALT values ≥ 2 times the baseline values and ≥ 3 X ULN, or ≥ 8 X ULN (whichever is smaller).

Concurrent with

- For patients with preexisting values of total bilirubin above the normal range: Total bilirubin level increased from baseline by an amount of at least 1 X ULN **or** if the value reaches ≥ 3 X ULN (whichever is smaller).

The patient should return to the investigational site and be evaluated as soon as possible, preferably within 48 hours from awareness of the abnormal results. This evaluation should include laboratory tests, detailed history, and physical assessment. The possibility of hepatic neoplasia (primary or secondary) should be considered.

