6.2. Safety Endpoints

Adverse Events:

Adverse Events (AEs) will be graded by the investigator according to the Common Terminology Criteria for Adverse Events (CTCAE) version 4.03 and coded using the Medical Dictionary for Regulatory Activities (MedDRA). For other AEs without specific CTC definitions, results are identified according to CTCAE “other” categories. Adverse events will be assigned to the appropriate cycle based on Day 1 of each cycle. Specifically, treatment emergent and treatment related AEs are defined as follows.

Treatment Emergent Adverse Events

- All deaths from start of treatment until 28 days after the final dose.
- All treatment related SAEs even if occurring after 28 days after the final dose or after EOT.
- All treatment unrelated SAEs from treatment start until 28 days after final dose of treatment.
- All treatment Non-fatal AEs occurring after treatment start up until 28 days after final dose of treatment.
- Disease progression is not considered a treatment emergent adverse event unless the subject dies of disease prior to 28 days after discontinuation of treatment.
- Events that are continuations of baseline abnormalities are considered treatment emergent adverse events only if there is an increase in grade over baseline.

Treatment Related Adverse Events

Treatment Related Adverse Events are treatment emergent adverse events with cause categorized by the investigator as related to study treatment. Events that are continuations of baseline abnormalities (signs and symptoms) are not considered treatment emergent, and therefore not considered treatment related, unless there is an increase in grade over baseline.

Laboratory Test Abnormalities:

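### Table 13 omits the return-to-baseline option that Section 5.4.5.1 gives for restarting glasdegib after a related Grade 3 or 4 non-hematologic toxicity

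*Protocol*

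**What the plan says.** Protocol Section 5.4.5.1 (Glasdegib) states the restart rule twice.

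- **Text.** A patient with a Grade 3 or 4 non-hematologic toxicity potentially attributable to glasdegib has "treatment interrupted regardless of when it occurs in the cycle until the toxicity resolves or returns to baseline" or is Grade 1 or less. The sentence refers to Table 13 for this.
- **Table 13, Grade 3 or higher row.** "Hold glasdegib until toxicity has recovered to" Grade 1 or less. Baseline is not mentioned and no footnote adds it. The dose then drops one level after a first episode and again after a second; a third means permanent discontinuation.

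The text adds a time limit: "If these parameters have not been met following >28 consecutive days of dose interruption, glasdegib should be permanently discontinued". If that happens, azacitidine alone may continue if the investigator sees clinical benefit and after discussion with the sponsor.

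Two other places use a recovery standard for glasdegib. Section 5.4.5 describes within-cycle interruption as lasting until adequate recovery, and Section 5.4.5.1, when it discusses follow-up assessments, explains that term as resolution or return to baseline. The third pre-defined safety event in Section 3.3 covers related Grade 3 or higher non-hematologic events "in the first cycle of treatment that have failed to recover to baseline or" Grade 1 or less by Day 49, where study treatment also had to be permanently discontinued.

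**The concern.** The text cites the table for a rule that the table does not contain. Investigators often dose from the table, so the cell is as operative as the paragraph. Take a patient who enters at Grade 2 for some non-hematologic term, has a first related Grade 3 event in that term, and settles back to Grade 2. Under the text, glasdegib restarts at 75 mg instead of 100 mg. Under the table it stays on hold, with no end in sight if Grade 2 is that patient's stable state. Two sites could treat identical patients in opposite ways, each in good faith.

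**Working it through.** The plan gives no figure to reproduce here. The check is to write both rules in the same terms, find where they part, and look for a clause that reconciles them.

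**The two rules.** Let b be the baseline grade of the toxicity and g its grade after recovery.

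- Section 5.4.5.1 text: restart if g ≤ max(b, 1).
- Table 13 cell: restart if g ≤ 1.

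| | g = 0 | g = 1 | g = 2 |
|---|---|---|---|
| b = 0 | both restart | both restart | both hold |
| b = 1 | both restart | both restart | both hold |
| b = 2 | both restart | both restart | **text restarts, table holds** |

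The rules differ in 1 of 9 cells. For b of 0 or 1, max(b, 1) = 1 and they are identical, so any disagreement needs a baseline of Grade 2 or higher.

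**The dose in the differing cell.** Table 12 lists 100, 75, 50 and 25 mg. A first episode at the 100 mg starting dose means one level down, so the text gives 75 mg and the table gives no drug.

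**Does any clause reconcile them?**

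- The clause allowing the investigator and sponsor to agree otherwise concerns the need for a dose reduction on resumption. It does not set the recovery threshold.
- The Medical Monitor clause covers deviations from the dose modifications. It does not say which threshold is the rule.
- Tables 14 and 15 deal with QTc prolongation and with muscle spasms and myalgia, all of which Table 13 excludes by its title.

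**Can such a patient be enrolled?** The expansion criteria do not generally exclude a Grade 2 baseline. Section 4.1.2 allows creatinine clearance down to 30 mL/min and exempts liver abnormalities due to the malignancy from the AST/ALT limit. The plan also expects abnormal baselines in general: Section 8.6.2 sets separate thresholds "For patients with preexisting AST or ALT baseline values above the normal range", and SAP Section 6.2 says "Events that are continuations of baseline abnormalities are considered treatment emergent adverse events only if there is an increase in grade over baseline". Neither passage shows how many patients, if any, start at Grade 2.

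**Which rule was meant?** The Section 5.4.5.1 rule, the explanation of adequate recovery in the same section (the term that Section 5.4.5 uses for ending an interruption) and the third safety event in Section 3.3 all include return to baseline. The Table 13 cell is the exception.

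**The case against.** The strongest objection is that this is a table cell shortening a rule that the paragraph citing it states in full. That largely stands. A reader might infer two competing dosing policies with the intent left open, but the running text points consistently to the baseline option. What remains is that nothing says the text prevails over the table, and a site using the table alone would not see the longer rule.

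Tables 14 and 15 might be offered as signs that a stricter rule was meant. They are weak evidence. Table 14 works in milliseconds and requires a return to 470 or less "msec and to within 20 msec of baseline in 7 days", a standard specific to QTcF. Table 15 does say "If event persists, hold dose until resolution to Grade" 1 or less in its Grade 2 column. Its Grade 3 column, however, lets the investigator restart one level lower even if the event has not reached Grade 1 within 3 weeks. It is therefore not an example of a strict Grade 1 rule.

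It is also fair to say that the case is rare and that a site in doubt can ask the Medical Monitor. An affected patient needs a baseline of Grade 2 or higher, a related event of Grade 3 or higher in the same term, and recovery to baseline but not to Grade 1. Both points limit the severity. Neither tells a site that follows either rule in good faith that there is anything to ask.

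**Conclusion.** The restart rule is internally contradictory and so wrong as written, with minor severity. It affects only patients with a baseline of Grade 2 or higher in the term concerned. The documents give no baseline grade distribution and no source for assuming a share, so no count is offered; it may be very small or zero.

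Two stronger conclusions are tempting and the documents do not support them.

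- **That such a patient must come off glasdegib after 28 days.** The limit attaches to the parameters in the text, and a patient back at baseline has met them. Permanent loss of the drug would follow only if a site wrongly ran that clock against the Table 13 threshold.
- **That the trial's results or stopping rules are affected.** The third safety event has its own recovery definition, which includes return to baseline, so a patient back at baseline by Day 49 does not count under it, whichever restart rule the site followed. The CR rate is computed on all treated patients in the cohort, and its definition does not depend on the restart rule.

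The conclusion rests on the current wording of Sections 3.3, 5.4.5 and 5.4.5.1.

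**What to change.** In the Grade 3 or higher row of Table 13, insert *baseline or* before the Grade 1 limit, so that the cell reads: *Hold glasdegib until toxicity has recovered to baseline or ≤ Grade 1*. This matches the paragraph that cites the table and the recovery wording of the third safety event in Section 3.3.

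The cost is two words in one cell. No visit, test or analysis changes.

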	At one lower dose level if mQTcF returns to ≤ 470 msec and to within 20 msec of baseline between 7-14 days and if no prior dose interruption related to mQTcF prolongation has occurred		x	x	
	At one lower dose level if mQTcF returns to ≤ 470 msec and to within 20 msec of baseline in 14 days if one prior dosing interruption related to mQTcF prolongation has occurred		x		
Management after dose resumed	An ECG should be repeated and mQTcF re-assessed approximately 7 days after glasdegib dosing resumption following interruption for a mQTcF prolongation		x	x	

Table 14. Glasdegib Dose Modifications for mean QTcF (mQTcF) Prolongation

Discontinue glasdegib permanently	The mQTcF prolongation does not return to ≤ 470 msec and to within 20 msec of baseline after 14 days		x	x	
	The Grade ≥ 2 mQTcF prolongation recurs after one dose reduction related to mQTcF prolongation		x	x	
	The Grade ≥ 3 mQTcF prolongation recurs after one prior dosing interruption related to mQTcF prolongation has occurred			x	
	If at any time during the 14 day window that glasdegib is stopped due to QTcF prolongation the patient has a confirmed mean QTcF interval > 515 msec or becomes symptomatic		x	x	

Dose modifications for glasdegib in case of drug class related AEs are outlined in [Table 15](#).

Table 15. Dose Modifications for Glasdegib in Case of Drug Class Related AEs

Muscle Spasms or Myalgia	Grade 1	Grade 2	Grade 3

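### Table 14 both restarts and permanently stops glasdegib for one pattern of Grade 2 QTcF recurrence, and nothing says which instruction prevails

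*Protocol*

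**What the plan says.** Section 5.4.5.1 makes Table 14 mandatory: above 480 msec, "Table 14 must be referenced and actioned". Under initial action, "Interrupt treatment" is ticked for Grades 2 and 3. All three resume rows require mQTcF to be back at or below 470 msec and within 20 msec of baseline. I number the rows in the order printed.

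- **R1** (Grades 2 and 3): recovery in 7 days with no earlier QTcF-related interruption. Resume at the same dose.
- **R2** (Grades 2 and 3): recovery to within 20 msec "of baseline between 7-14 days and if no prior dose interruption related to mQTcF prolongation has occurred". Resume one level lower.
- **R3** (Grade 2 only): recovery to within 20 msec "of baseline in 14 days if one prior dosing interruption related to mQTcF prolongation has occurred". Resume one level lower.
- **D1** (Grades 2 and 3): no recovery after 14 days. Stop permanently.
- **D2** (Grades 2 and 3): Grade 2 or higher "mQTcF prolongation recurs after one dose reduction related to mQTcF prolongation". Stop permanently.
- **D3** (Grade 3 only): Grade 3 or higher recurs after one QTcF-related interruption. Stop permanently.
- **D4** (Grades 2 and 3): confirmed mean QTcF above 515 msec, or symptoms, "at any time during the 14 day window that glasdegib is stopped due to QTcF prolongation". Stop permanently.

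The table has no note ranking the resume and discontinuation blocks. Section 7.6 only sends the reader back to Table 14.

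**The concern.** R3 has a single history condition, one earlier interruption, and does not exclude a patient whose dose was already reduced for QTcF. D2 is written for exactly that patient. A site that reads the resume block first could restart a QT-prolonging drug at 50 mg in someone whom D2 takes off it.

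QT prolongation has been seen with this combination. Section 1.2.13.2 reports it as a treatment-emergent event in 4 of 11 lead-in patients, one of whom stopped treatment for Grade 3 prolongation related to glasdegib.

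The restart would be recorded, through the AE rules in Sections 8.5 and 8.14.2 and the dose-change documentation in Section 5.4.5.1. No required step would automatically catch it beforehand:

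- SAE reporting is compulsory only above Grade 2 (Section 8.6.1).
- Sponsor approval is needed only below 50 mg.
- Medical Monitor agreement is needed for deviations, and a restart that follows R3 need not look like one to the site.
- Cardiology consultation is compulsory from 501 msec. Below that, "Additional ECG and cardiac consultation should be obtained if clinically indicated".

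**Working it through.** No figure in the plan needs reproducing. The check applies the rows literally to two-episode histories. I assume that the first episode ends in resumption and that D4 is not triggered.

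**State after episode 1.** Recovery in 7 days (R1) leaves 1 interruption and 0 reductions. Recovery at 7-14 days (R2) leaves 1 interruption and 1 reduction. The first-episode grade does not matter, because R1 and R2 are ticked for both grades.

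**Rows met at episode 2.** R1 and R2 are closed because an interruption has already occurred. There are 2 × 2 × 2 = 8 patterns: first recovery, second grade, and second recovery within 14 days or not.

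| First recovery | Second grade | Recovers within 14 days | Resume rows met | Discontinuation rows met |
|---|---|---|---|---|
| in 7 days | 2 | yes | R3 | none |
| in 7 days | 2 | no | none | D1 |
| in 7 days | 3 | yes | none | D3 |
| in 7 days | 3 | no | none | D1, D3 |
| 7-14 days | 2 | yes | **R3** | **D2** |
| 7-14 days | 2 | no | none | D1, D2 |
| 7-14 days | 3 | yes | none | D2, D3 |
| 7-14 days | 3 | no | none | D1, D2, D3 |

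One pattern of 8 meets both blocks. R3 applies on 2 patterns, so it conflicts on 1 of those 2. A finer split, keeping first-episode grade and three classes of second recovery, gives 2 × 2 × 2 × 3 = 24 sequences. Of these, 4 overlap, and all 4 belong to the same pattern.

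**Dose consequence**, starting at 100 mg, with levels 100, 75 and 50 mg, no other reductions and Grade 2 recurrences:

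- First recovery in 7 days: 100, 100, 75 mg, stop at episode 3. One reduction on either reading.
- First recovery at 7-14 days, R3 followed: 100, 75, 50 mg, stop at episode 3. Two reductions.
- First recovery at 7-14 days, D2 followed: 100, 75 mg, stop at episode 2. One reduction.

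**Text that might settle the order.** The worst-toxicity rule in Section 5.4.5 concerns several toxicities at once, not two rows for one toxicity. Table 13 excludes QTc. The general allowance of up to two dose levels in Section 5.4.5.1 depends on the type and severity of toxicity; it is a ceiling, but it does not rule out a second reduction to 50 mg. Section 6.4 is silent on this point.

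**The case against.** The strongest reply is that the table ranks itself. D2 is met at the onset of the recurrence, whereas R3 can be tested only after recovery. By then a permanent stop already applies, and restarting contradicts it. D4 supports this reading: a first-episode patient above 515 msec who recovers within 14 days also meets R1 or R2, so D4 has an effect only if discontinuation overrides. On that reading R3 keeps a role, for patients who resumed at the same dose. These points stand as evidence of intent, and I accept that stopping is the likely intent.

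They do not amount to a written rule. R3 as printed covers the already-reduced patient, and the discontinuation block comes after the resume rows. The interruption tick does not decide the matter either way, since a hold is compatible with a later permanent stop.

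It is also fair to say that the hazard is limited. Section 1.2.20 gives a predicted mean QTcF change of 5.30 msec at the mean peak concentration for 100 mg. In the thorough QT study the largest upper 90% confidence bound was 15.6 msec, at the supratherapeutic dose, below the 20 msec threshold of concern. A restart under R3 follows recovery, is at a lower dose, and is followed by a check: "An ECG should be repeated and mQTcF re-assessed approximately 7 days after glasdegib dosing resumption". Section 5.4.5.1 also lets a site stop glasdegib for any reason under good clinical practice. This lowers the stakes but leaves the two instructions in conflict.

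**Conclusion.** Wrong as written, and minor. For a first episode recovering at 7-14 days followed by a Grade 2 recurrence recovering within 14 days, Table 14 directs both a restart one level lower and a permanent stop, and neither the table nor the related sections rank them. The size is 1 of 8 rule patterns under the assumptions above; the count depends on how patterns are grouped and is not a frequency. From 100 mg, the difference for an affected patient is one extra restart, at 50 mg. The documents give no recurrence rate, so the number of patients is unknown and probably small. No efficacy analysis, sample size or stopping rule is affected.

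**What to change.** 1. In R3, add the condition that no earlier dose reduction related to mQTcF prolongation has occurred. The row then serves only patients who resumed at the same dose after the first episode.
2. Add a note to Table 14 that any permanent-discontinuation criterion takes precedence over the resume rows. This also settles the overlap between D4 and R1 or R2.

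With the first change, 0 of the 8 patterns overlap and 0 are left without an instruction, and at most one QTcF-related reduction is possible. The cost is one condition, one table note and a clarification to sites. No assessments are added and the analysis does not change.
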